8.3 Hospitalizations

Post-baseline research assistant (RA) collected hospitalizations will be summarized by treatment arm. The number of hospitalizations, the number of patient participants with hospitalizations, and the number of hospitalizations per patient participant (both numerically and categorically (0, 1, 2, 3, 4, and 5 or more visits)) will be presented. A listing of hospitalizations by treatment arm will be generated. The listing will include Site, Participant ID, date of enrollment, date of hospitalization, discharge date, primary, secondary, and tertiary diagnosis/complaint, severity, and outcome.

8.4 Emergency Department Visits

Post-baseline RA collected ED visits will be summarized by treatment arm. The number of ED visits, the number of patient participants with ED visits, and the number of ED visits per patient participant (both numerically and categorically (0, 1, 2, 3, 4, and 5 or more visits)) will be presented. A listing of ED visits by treatment arm will be generated. The listing will include Site, Participant ID, date of enrollment, date of ED visit, discharge date, primary, secondary, and tertiary diagnosis/complaint, severity, and outcome.

8.5 Death

[figure not shown]
A listing of deaths by treatment arm will be presented and will include Site, Participant ID, date of enrollment, date of death, source of death report, primary, secondary, and tertiary cause of death, and MedDRA® coded preferred term and system organ class. Narratives of deaths will also be provided.

9.0 SIGNIFICANCE TESTING AND MULTIPLICITY

The primary outcome will be evaluated using a two-sided test with a type I error rate of 5%. There are several secondary outcomes; however, adjustments for multiple comparisons will not be performed since these are not part of the study's primary objective. The resulting p values will be interpreted appropriately in the context of the multiple tests being performed. Effect estimates will be presented with confidence intervals, and interpretation of hypothesis tests for multiple secondary outcomes will take into consideration the number of tests that were performed. Reporting of results will be transparent, with null as well as significant findings reported.

10.0 SAMPLE SIZE AND POWER

Power was based on simulations exploring four possible scenarios to consider different time trends of the intervention effect as well as possible assessment impact in the control group. Assessment impact means that the repeated monthly assessments alone could lead to a decrease in the control group in the response variable. The four scenarios are depicted in Figure 5. This figure shows the mean values of unhealthy days (within the past 90 days) assumed in each arm at 0, 3, and 6 months. The mean in the control arm is expected to be between 10 and 20, and 20 was selected for simulations because it is the most conservative (i.e., gives the lowest power), assuming that the additive effect size does not change as the control group mean changes. Scenario 1 has a 6-day constant difference between groups at both time points; in scenario 2 the intervention effect wanes to a 5-day difference during months 4-6. Scenarios 3 and 4 are the same as 1 and 2, but with assessment impact included, decreasing the mean by an additional 1 day per 90 days in each arm.

10.1 Figure 5: Mean Values in Treatment and Control Groups for Four Different Simulation Scenarios

Numbers of days of risky opioid use for each patient participant are drawn from binomial distributions for the two 90-day time intervals. The size parameter of the binomial distribution is 90. The probability parameter is the specified mean number of days divided by 90, but also includes a PCP intercept (randomly drawn from a normal distribution with mean zero and variance 0.15) and an individual intercept (randomly drawn from a normal distribution with mean zero and variance 0.25). The PCP intercepts induce within-PCP correlation of simulated responses. The individual intercepts create overdispersion to more realistically reflect individual variability. The overdispersed distribution may be more appropriately modelled with a negative binomial distribution than a binomial or poisson distribution. The variance parameters were selected to be conservative and to generate data with most values less than 30 and few values over 45 (per 90 days). The PCP variance parameter describes how much the PCP-specific mean values tend to vary from each other (which is a reflection of the Intra Class Correlation (ICC)). With the specified parameters, the middle 50% of the PCP-specific means in the control arm lie between 17 and 25. The true within-PCP correlation is not known for this outcome, but this is expected to be an upper limit on the expected variability of the PCP-specific means so should provide a conservative power estimate. For each simulated data set, a negative binomial model was fit with random PCP intercepts and a fixed treatment effect. One thousand iterations were performed per scenario. Power was estimated as the proportion of simulated data sets with significant ($p \leq 0.05$) treatment effect estimates based on a two-sided test.

The original protocol planned to enroll 60 PCPs with approximately 8 participants per PCP. As of November 2021, recruitment challenges led to our re-evaluating whether a reduced sample size was possible with minimal impact to power. Additional simulations were run to examine various conditions of number of PCPs and patient participants per PCP, with 20% participant dropout assumed for all simulations. The original power estimates are provided for completeness and to show there is minimal loss of power when modifying the assumptions related to number of PCP and patient participants.

Table 6 shows power for the two outcomes in the four simulated scenarios described above, under four conditions (A-D) of number of PCPs and patient participants per PCP.

Condition A shows the power for the original situation of 60 PCPs and 8 participants per PCP, with Conditions B and C illustrating the impact to power when keeping the number of PCPs at 60 but reducing the number of participants per PCP to 4 or 5. As a sensitivity analysis, we also examined the situation in which 50 PCPs had 4 participants each (Condition D), which we believe is a worst case scenario in which less than 60 PCPs are contributing patients and those that do have participants enrolled from their panel have fewer than the expected 5.

Effect of time trends of the intervention effect and possible assessment impact in the control group: The additive treatment effect for the 180-day period is the sum of the 90-day additive effects for the two 3-month time intervals. For example, Scenario 1 indicates 90-day means of 20 and 14 in the two groups at both the 3- and 6-month time points, which translate into 180 day means of 40 and 28 in the two groups, so a treatment effect of -12 days. In scenarios 2 and 4, the waning of the effect causes this outcome to lose power. The scenarios with assessment impact have more power because there is higher power for lower control group mean values due to lower variability of the binomial distribution for a lower probability parameter (and because we are assuming equal assessment impact between the two groups). If the impact were higher in the control group, the treatment effect would be reduced, reducing power.

10.2 Table 6: Power Estimates Based on 1000 Simulations

Condi- tion	No. of PCPs	No. of pts per PCP	Scenario	Group means (3-mo, 6-mo)		Power
				Control	Treatment	
A	60	8	1: Constant effect, no assessment impact	20, 20	14, 14	0.98
			2: Waning effect, no assessment impact	20, 20	14, 15	0.95
			3: Constant effect, assessment impact	19, 18	13, 12	0.99
			4: Waning effect, assessment impact	19, 18	13, 13	0.97
B	60	4	1: Constant effect, no assessment impact	20, 20	14, 14	0.97
			2: Waning effect, no assessment impact	20, 20	14, 15	0.93
			3: Constant effect, assessment impact	19, 18	13, 12	0.97
			4: Waning effect, assessment impact	19, 18	13, 13	0.95
C	60	5	1: Constant effect, no assessment impact	20, 20	14, 14	0.97
			2: Waning effect, no assessment impact	20, 20	14, 15	0.93
			3: Constant effect, assessment impact	19, 18	13, 12	0.99
			4: Waning effect, assessment impact	19, 18	13, 13	0.97
D	50	4	1: Constant effect, no assessment impact	20, 20	14, 14	0.93
			2: Waning effect, no assessment impact	20, 20	14, 15	0.89
			3: Constant effect, assessment impact	19, 18	13, 12	0.94
			4: Waning effect, assessment impact	19, 18	13, 13	0.91

Note: All simulations assume 20% dropout.

Within the anticipated range of mean values (10-20 days per 90), power increases as the control group mean decreases. Therefore, power would be even higher if the control group mean is 10 or 15 instead of 20, as long as the additive decrease remains the same (-6 days per 90). Additionally, power will be higher if the additive decrease is higher than planned.

Effect of Reducing Number of PCPs and patient participants per PCP: All scenarios and conditions presented have power in the range of 89% - 99%, allowing us to conclude that 1) reducing number of patient participants for each of 60 PCPs has minimal impact to power; and 2) even if 50 PCPs enrolled 4 participants each for a total of 200 participants, power is still in the acceptable range across all scenarios of time trends of the intervention effect and assessment impact in the control group.

11.0 INTERIM ANALYSES AND DATA MONITORING

No interim analyses were planned.

12.0 DATA QUALITY

12.1 Data Audits

A summary of data audit results from site interim monitoring visits conducted by Clinical Coordinating Center (CCC) monitors will be presented by site, including total fields audited, total data discrepancies, and error rate.

12.2 Protocol Deviations

Protocol deviations will be summarized by site and will include the number of deviations reported, the number of patient participants each deviation affects, frequencies for the types of protocol deviations, and information on whether the protocol deviation was deemed minor or major. A detailed listing of protocol deviations by deviation category will be provided.

13.0 SOFTWARE TO BE USED FOR ANALYSES

All analyses described in this document to be performed by the DSC will use SAS® Version 9.4 software. R-studio was used for the sample size estimation and sample size re-estimation.

14.0 ADDENDUM

14.1 Zero-Inflated Negative Binomial Model for the Primary Outcome

CTN-0101 is a prevention study, enrolling individuals who have risky opioid use but do not meet DSM-5 diagnostic criteria for a moderate or severe opioid use disorder (OUD). As such, it is anticipated that some participants may avoid all risky opioid use during the primary outcome measurement period. This is expected to result in an excess of zero-use days (i.e., zero-inflation) in the sample. In this case, the treatment effect may be in two forms: 1. Higher likelihood for people to have no risky opioid use; and 2. Lower days of use for people with non-zero days of risky opioid use.

To investigate this, as a post hoc analysis to the primary outcome analysis, a zero-inflated negative binomial (ZINB) model will be fit for the primary outcome data. The ZINB model accounts for excess zeros by assuming that they arise from a mixture of two processes: (1) participants who completely avoided risky opioid use during the treatment period, and (2) participants who did not completely avoid risky opioid use during the treatment period but may still have reported zero days of opioid use during this period. This model provides two estimates of the treatment effect: an odds ratio for “completely avoiding opioid use” and a rate ratio for the number of days of risky opioid use. The treatment effects of STOP from this model will be given as 1) an odds ratio, the

exponentiated estimate of the treatment effect from the logit model, along with a 95% confidence interval, and 2) a rate ratio, the exponentiated estimate of the treatment effect from the negative binomial model, along with a 95% confidence interval. Additionally, the overall treatment effect will be estimated using the shared parameter marginal ZINB (SPMZINB) model [14]. The treatment effect of STOP from this model will be given as a rate ratio, the exponentiated estimate of the treatment effect, along with a 95% confidence interval. Both models will be fit in SAS using Proc GENMOD (ZINB model) and Proc NL MIXED (SPMZINB model) and will use the multiply imputed primary outcome datasets. The results from these models will be used to explore the extent and impact of zero-inflation in the primary outcome for this study.

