7.0 EFFICACY ANALYSIS

7.1 Definition of the Primary Outcome Measure

The primary outcome (H1.1) measure is self-reported number of days of risky (illicit or nonmedical) opioid use in the past 180 days, assessed at 6 months after the baseline visit using single items based on questions used in the Addiction Severity Index (ASI) [3,4], and Current Opioid Misuse Measure (COMM) [5,6]. Participants are asked to specify the number of days of illicit opioid use and of nonmedical opioid use in the past 30 days (range is 0-30 days). Illicit opioid use includes use of heroin or synthetic opioids. Nonmedical opioid use includes using prescribed opioids more than prescribed (e.g., taking 2 tablets when the prescription indicates a dose of 1 tablet) or taking pharmaceutical opioids that were not prescribed to the individual taking them. Prescription opioids may be prescribed by the participating PCP or by another medical provider. The measure is calculated as the sum of all days of use reported on the assessments of past 30-day drug use for the first 6 months (i.e., the sum of days of use from the measures collected on day 30, day 60, day 90, day 120, day 150, and day 180).

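### The zero-inflated model's odds ratio in SAP 14.1 describes a latent excess-zero class, not reporting no risky opioid use; it needs relabelling and a direct zero-versus-any-use model beside it

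*SAP*

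**What the plan says.** SAP 14.1, added in version 2.0, expects an excess of zeros and names two forms the STOP effect may take: "Higher likelihood for people to have no risky opioid use" and "Lower days of use for people with non-zero days of risky opioid use". It then plans, "as a post hoc analysis to the primary outcome analysis, a zero-inflated negative binomial (ZINB) model will be fit" to the primary outcome data. The zeros are described as a mixture: one class avoided risky use entirely, and the other consists of "participants who did not completely avoid risky opioid use during the treatment period but may still have reported zero days of opioid use". The model is said to give "an odds ratio for “completely avoiding opioid use” and a rate ratio for the number of days of risky opioid use", each with a 95% confidence interval. For the combined effect, "the overall treatment effect will be estimated using the shared parameter marginal ZINB (SPMZINB) model". Both models use the multiply imputed datasets, and the stated purpose is to explore the extent and impact of zero-inflation.

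The outcome is defined in SAP 7.1: "The measure is calculated as the sum of all days of use reported on the assessments of past 30-day drug use" over the first six monthly surveys. A total of zero therefore means that no risky day was reported in any of the six surveys.

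No other analysis compares a zero total with a non-zero one. The output list in SAP 17.0 has no such table, the Table 41 shell gives only N, mean, SD, minimum, median and maximum, and H2.6 concerns increases from baseline.

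**The concern.** Effect 1 is about a quantity that can be read from the data: whether the 180-day total is zero. The ZINB logit part does not model that quantity. It models membership of a class whose members are always zero, after the count part has claimed some of the zeros for itself. How many it claims is set by the fitted shape of the negative binomial, not by anything recorded about the participant. The count-part rate ratio likewise averages over that part's own zeros, so strictly it is not the effect among people with non-zero days.

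The addendum is meant to show whether STOP works through abstinence or through fewer days among users. If a reader takes the logit odds ratio as the effect on having no risky use, its size may be misread. If dispersion is high, it may also be too imprecise to show an effect that a direct comparison would show.

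**Working it through.** **Nearest planned figure.** SAP 14.1 states no power. The closest figure is SAP 10.2 Table 6, Condition C, scenario 1: 0.97. Re-simulating the SAP 10.0 design (binomial of size 90 per interval, PCP variance 0.15 and individual variance 0.25, taken on the logit scale) with a negative binomial model, a random PCP intercept and 4 analysed per PCP (5 less 20%) gives 0.955, with Monte Carlo SE about 0.01. That is close enough to use the same simulation to see what dispersion it implies.

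**Dispersion implied by SAP 10.0.** Moment estimate: k = (SD² − mean)/mean².
- Control: 180-day mean 43.1, SD 20.5, so k ≈ (420.3 − 43.1)/1857.6 = 0.20.
- STOP: mean 31.1, SD 16.7, so k ≈ (278.9 − 31.1)/967.2 = 0.26 (0.255 before rounding).

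A negative binomial with these values gives a zero probability below 0.001. That simulation contains essentially no zeros, whereas 14.1 expects an excess of them.

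**Assumptions for 14.1.** The documents give neither the zero share nor the dispersion of the count part. Assumed: structural zeros π of 20% (EUC) and 35% (STOP); k from 0.3 to 3; means 40 vs 28 (SAP 10.0, scenario 1), and lower means of 15 vs 10.5 with the same ratio of 0.70.

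**Formulas.**
- Latent odds ratio: (0.35/0.65)/(0.20/0.80) = 2.15, whatever k is.
- Observed zero: P(Y=0) = π + (1 − π)(1 + kμ)^(−1/k).
- Ratio of means among users: [μ_STOP/(1 − p_STOP)]/[μ_EUC/(1 − p_EUC)], with p = (1 + kμ)^(−1/k).

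**Worked case, k = 3, means 40 vs 28.**
- Count-part zeros: 121^(−1/3) = 0.202 and 85^(−1/3) = 0.227.
- P(Y=0): 0.20 + 0.80 × 0.202 = 0.362 and 0.35 + 0.65 × 0.227 = 0.498.
- Observed-zero odds ratio: (0.498/0.502)/(0.362/0.638) = 1.75, against 2.15 latent.
- Users' ratio: (28/0.773)/(40/0.798) = 0.72, against a count-part ratio of 0.70.

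**Simulated power**, 300 patients, two-sided 5%, 500 data sets per row. There is no clustering, covariate or imputation, and the latent odds ratio is 2.15 in every row.

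| Means | k | Observed-zero OR | Users' ratio | Logistic on observed zero | ZINB OR, Wald | ZINB OR, likelihood ratio |
|---|---|---|---|---|---|---|
| 40 vs 28 | 0.3 | 2.16 | 0.70 | 0.85 | 0.85 | 0.85 |
| 40 vs 28 | 1 | 2.11 | 0.71 | 0.84 | 0.80 | 0.81 |
| 40 vs 28 | 2 | 1.90 | 0.72 | 0.73 | 0.58 | 0.63 |
| 40 vs 28 | 3 | 1.75 | 0.72 | 0.66 | 0.33 | 0.49 |
| 15 vs 10.5 | 0.3 | 2.17 | 0.70 | 0.84 | 0.83 | 0.83 |
| 15 vs 10.5 | 1 | 2.06 | 0.72 | 0.83 | 0.69 | 0.71 |
| 15 vs 10.5 | 2 | 1.82 | 0.73 | 0.73 | 0.37 | 0.53 |
| 15 vs 10.5 | 3 | 1.69 | 0.735 | 0.61 | 0.17 | 0.35 |

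With no effect on counts, the observed-zero odds ratio at k = 3 falls to 1.64 (mean 40) or 1.59 (mean 25), and at k = 1 it is 2.05 or 2.00. For mean 40 and k = 3, power is about 0.59 (direct) vs 0.31 (ZINB, Wald). It becomes 0.55 vs 0.45 once totals are capped at 180 days.

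**The case against.** The other side has real weight.

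- **High dispersion is an assumption.** The SAP's own simulation implies about 0.20 to 0.25, where the two odds ratios coincide and no power is lost. At k = 3 and mean 40, an uncapped negative binomial puts about 4.8% of values above 180 days, which the monthly cap of 30 in SAP 7.2.1 rules out. This stands as a limit on the size. It does not settle the matter, because a simulation with practically no zeros is a weak guide to data expected to have many.
- **A second-class zero is not meaningless.** It may be a participant with a continuing tendency to use who had no risky day, or one who under-reported. The outcome is self-reported, and Protocol 6.1 acknowledges social desirability bias. This stands, but the shape of the counts cannot tell those participants from true avoiders, and effect 1 is not worded as a latent tendency.
- **Purpose.** 14.1 also sets out to explore zero-inflation, which a two-part model does not measure. This is a sound reason to keep the ZINB.
- **Status.** The analysis is post hoc, promises estimates with intervals and no power target, and has a separate marginal model for the overall effect. This stands and lowers the stakes.

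A reader might infer that the ZINB inflates the abstinence effect. It does not: in the 300-patient runs with 20% vs 35% structural zeros, its median odds ratio was about 2.1 to 2.2, at its own target of 2.15. The difference is between two estimands, so the fault lies in the label. A reader might also infer that no-use is known for everyone. SAP 7.2.3 allows for up to 20% missing the endpoint, so some zeros depend on imputation.

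**Conclusion.** The labelling point holds at any dispersion: the ZINB logit odds ratio is for an excess-zero class, and calling it an odds ratio for complete avoidance is inaccurate. Its numerical effect depends on quantities the documents do not give. Under the assumed 20% vs 35% structural zeros, the two odds ratios nearly agree at dispersion 1 or below (2.15 vs 2.0 to 2.17), with at most a modest power loss (largest 0.83 to 0.69). At dispersion 2 to 3 they part (2.15 vs 1.6 to 1.9), and the Wald loss runs from about a fifth (0.73 to 0.58) to about 70% (0.61 to 0.17). It is smaller with capped totals or a likelihood-ratio test.

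Two stronger readings are not supported. One is that the model estimates neither effect in any useful sense: for effect 2 the gap is at most 0.70 vs 0.735, and for effect 1 it disappears at low dispersion. The other is a fixed figure such as half the power: that is neither derivable from the documents nor a bound. These simulations omit PCP clustering, covariates and imputation. The primary analysis in SAP 7.2.2 is untouched.

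**What to change.** In SAP 14.1:

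1. Keep the ZINB and the marginal model as exploratory analyses, and relabel the ZINB odds ratio *odds of excess-zero class membership*.
2. Add, as the estimate for effect 1, a logistic mixed model of zero versus at least one risky day in Months 1-6, with a PCP random intercept, site and baseline days, matching the terms in SAP 7.2.2.
3. Optionally add a zero-truncated negative binomial with the same terms for days among users, labelled descriptive because that group is formed after randomisation.
4. State how imputed months are classed. The imputation code in SAP 7.2.3 bounds monthly values at 0 and 30 but does not round, so an imputed month will almost never be exactly zero. Nearly everyone with an imputed month would then count as a user, and the ZINB loses the same zeros. One workable rule: any observed risky day counts as use, imputed months are rounded to whole days, and a complete-case version is shown as a check.

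Cost: addendum wording and one or two extra standard models in an analysis already labelled post hoc. No new data are needed. Replacing the ZINB outright is not advised, since that would drop the exploration of zero-inflation.

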2.3.3 Treatment Randomization

This is a cluster-randomized trial in which PCPs are the clusters. In study sites where PCPs practice in teams, randomization will be at the team level (for example, if PCPs practice in teams of two, the two PCPs will be treated as one cluster in the randomization). PCPs will be randomized, stratified by site, in a 1:1 fashion to the STOP or EUC condition.

Patient participants enrolled in the study will receive STOP or EUC according to the assignment of their PCP.

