7.2.2 Statistical Analysis Methods for Primary Outcome

Because the most intensive intervention period is during the initial 3-4 months, the primary outcome is measured at 180 days (6 months) to capture the main intervention effect. Given the primary outcome is the number of days of risky opioid use within the first 180 days following the baseline assessment collected with HLM, a mixed effects negative binomial model with a log link will be fit to estimate the difference in means between treatment and control groups. Fixed effects include treatment effect, site effect, and the baseline value of the response variable (days of use within 30 days prior to the baseline assessment timepoint), which may improve precision. Random PCP intercepts are to account for within-PCP correlation of participant response values. Since randomization was at PCP team level where PCPs practiced in teams and shared patients regularly, PCP cluster was specified as PCP/PCP team which was the unit of randomization, that is, if two or more PCPs are randomized as a single cluster, they will be analyzed as a single cluster. Letting Y_{jk} denote the response variable of a participant in site j with PCP k , treatment denotes a binary treatment indicator variable, site denotes a multi-level categorical variable representing study sites, and baseline denote the baseline value, the formula for the log-transformed expectation of Y_{jk} is given:

$$\log[E(Y_{jk})] = \beta_0 + \beta_1 \cdot \text{treatment} + \beta_2 \cdot \text{baseline} + \beta_3 \cdot \text{site} + \gamma_k,$$

where γ_k is normally distributed with mean zero and standard deviation σ_γ representing random effect by within-PCP correlation of participant responses. The negative binomial model allows for potential overdispersion of the response variable, so is more flexible than a Poisson distribution which would require the mean to be equal to the variance.

The primary hypothesis will be evaluated by testing whether the treatment effect, β_1 , is different from zero. This is equivalent to testing whether the control mean is different from the intervention mean.

The template SAS code for the primary analysis is:

```
PROC GLIMMIX DATA=dat METHOD=quad;
  CLASS PCP treat site;
  MODEL daysin180 = treat site baseline / solution DIST=negbin LINK=log ddfm=bw;
  RANDOM intercept / SUBJECT= PCP;
RUN;
```

Where:

“dat” is the name of the dataset with one row per patient participant,

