This table will be repeated by visit and prescription for opioids in the past 6 months (yes/no) as reported on the COMM. The table will present the number and percentage of participants at that visit that reported having an opioid prescription in the past 6 months. If a patient participant does not complete the COMM assessment at that visit, the previous COMM response will be used to determine if the patient participant has an opioid prescription. For example, if the patient participant does not do the 12-month COMM assessment but has a 12-month UDS, the COMM response from the 6-month visit will be used to categorize the participant at the 12-month visit. If

the patient participant does not have any COMM responses from the baseline, 6 or 12-month visits but has UDS collected for those visits, it will be assumed the patient participant does not have an opioid prescription for any of the visits.

The following analysis will be done by the LN:

The proportions of individuals whose average number of days (within 30 days) of illicit or nonmedical opioid use during 180 days of follow-up increased relative to their baseline measure (days of use in the 30 days before the baseline assessment, H2.6) will be compared between groups at 6 months and 12 months using chi-square test respectively.

Descriptive summary statistics for COMM score assessed at screening and at 6 and 12 months (H2.7 h), Comparisons of the secondary outcomes between the two treatment arms will be conducted using t-tests or Mann-Whitney tests for continuous measures, chi-square tests for categorical measures.

Generalized estimating equations (GEE) to account for correlation of responses within PCP cluster will be fit for the incidence of moderate to severe OUD (defined as a score of at least 4 on the CIDI, H2.8) and drug use disorder (PDSQ drug items, H2.9) and alcohol use disorder (PDSQ alcohol items, H2.9) assessed at 6 and 12 months separately. Treatment effect is estimated adjusting for baseline level of each measurement. Time trend is evaluated using a time variable.

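### The post hoc zero-inflated model in SAP 14.1 names no PCP-cluster term, so its rate-ratio confidence interval is too narrow as written

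*SAP*

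**What the plan says.** SAP 2.3.3 sets the unit of randomisation: "This is a cluster-randomized trial in which PCPs are the clusters". Where PCPs work in teams, the team is the cluster.

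For the primary outcome, SAP 7.2.2 specifies a mixed effects negative binomial model with treatment, site and baseline days of use, and adds: "Random PCP intercepts are to account for within-PCP correlation of participant response values". The SAS code there and in SAP 7.2.3 has a random intercept by PCP. For the use-disorder outcomes (H2.8 and H2.9), SAP 7.8 is equally explicit: "Generalized estimating equations (GEE) to account for correlation of responses within PCP cluster will be fit".

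SAP 14.1, added in version 2.0, refits the primary outcome "as a post hoc analysis to the primary outcome analysis". It promises three treatment effects, each with a 95% confidence interval: an odds ratio and a rate ratio from the ZINB, and an overall rate ratio from the SPMZINB. On method it says "Both models will be fit in SAS using Proc GENMOD (ZINB model", assigns the SPMZINB to Proc NLMIXED, and states that both "will use the multiply imputed primary outcome datasets". It gives no equation, code or list of covariates. It names no PCP effect, estimating-equation approach or robust variance, and does not refer back to the terms of SAP 7.2.2.

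**The concern.** Patients of the same PCP share an arm and, on the SAP's own power assumptions, resemble each other. The zero-inflated fit in Proc GENMOD has no random-effect term, so a programmer who follows SAP 14.1 literally will treat these patients as independent. The reported standard error then leaves out the between-PCP variation that the randomisation builds into the treatment comparison.

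Multiple imputation does not put it back. The imputation code in SAP 7.2.3 uses treatment, site, baseline and the six monthly values but not PCP, and the pooling rules add variance for missing data only.

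The stake is interpretation. The addendum is meant to show how much zero-inflation there is and what it does to the result, so its intervals will be set beside the primary rate ratio, whose interval does allow for PCP. If the ZINB interval is tighter, or excludes 1 when the primary one does not, nobody can tell whether modelling the zeros or dropping the cluster term is responsible.

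**Working it through.** **Inputs from the documents**
- 60 PCPs with 5 patients each: Protocol 2.1.2; SAP 10.2, Condition C.
- Control mean of 20 days per 90, so 40 per 180: SAP 10.0.
- Between-PCP variance 0.15 and between-patient variance 0.25: SAP 10.0, which calls the PCP figure an expected upper limit and says that the true correlation is unknown.
- 20% dropout: note under the SAP 10.2 table. It is not applied to the ZINB runs, because the addendum uses imputed data and so close to all 300 patients.

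**Assumed, because the documents give no figure**
- 20% or 40% structural zeros.
- PCP variance in the logit of being a structural zero: 0, 0.05, 0.15 or 0.5.
- Lower PCP variances of 0.05 and 0.02 for the counts.

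**Step 1: reproduce the plan's figures.** Each patient has two Binomial(90, p) counts, with logit(p) = logit(mean/90) + PCP effect + patient effect. This gives quartiles of the PCP means of 17.2 and 25.2, against 17 and 25 in SAP 10.0. For the negative binomial model with a PCP intercept, power in Condition C with all 300 analysed is 0.978, 0.92, 0.987 and 0.958 in Scenarios 1–4, against 0.97, 0.93, 0.99 and 0.97. With 20% removed at random, Scenario 1 gives 0.967 (600 runs) and 0.93 (300 runs), pooled 0.955. Scenario 2 then gives 0.90 against 0.93. The data model is close enough for the present purpose.

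**Step 2: expected size from the design effect.** With p = 40/180 = 0.222, the binomial variance on the logit scale is 1/(180 × 0.222 × 0.778) ≈ 0.03. The intraclass correlation is then about 0.15/(0.15 + 0.25 + 0.03) ≈ 0.35. The design effect is 1 + (m − 1) × 0.347: 2.04 for m = 4 and 2.39 for m = 5. The standard error should be too small by a factor of √2.04 = 1.43 to √2.39 = 1.55.

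**Step 3: plain negative binomial, no treatment effect, 700 runs per setting.** Ranges cover 20% loss and all 300 analysed.

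| PCP variance | Model | Type I error | True SD / reported SE |
|---|---|---|---|
| 0.15 | no PCP term | 0.179–0.194 | 1.44–1.52 |
| 0.15 | PCP intercept | 0.053–0.064 | – |
| 0.05 | no PCP term | 0.114 | 1.24–1.26 |
| 0.02 | no PCP term | 0.074–0.079 | 1.09–1.10 |

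This agrees with step 2 and shows that the PCP intercept brings the error back to near 5%.

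**Step 4: the ZINB itself, no PCP term, no treatment effect, all 300 analysed, 700 runs per row**

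| Zeros | PCP variance, counts | PCP variance, zero part | Rate ratio: type I error (SD/SE) | Odds ratio: type I error (SD/SE) |
|---|---|---|---|---|
| 20% | 0.15 | 0 | 0.177 (1.43) | 0.041 (1.00) |
| 20% | 0.15 | 0.15 | 0.186 (1.43) | 0.060 (1.04) |
| 20% | 0.15 | 0.5 | 0.171 (1.43) | 0.079 (1.12) |
| 20% | 0.05 | 0.05 | 0.126 (1.25) | 0.039 (0.98) |
| 40% | 0.15 | 0 | 0.139 (1.33) | 0.040 (0.95) |
| 40% | 0.15 | 0.15 | 0.163 (1.35) | 0.076 (1.06) |
| 40% | 0.15 | 0.5 | 0.151 (1.35) | 0.086 (1.16) |
| 40% | 0.05 | 0.05 | 0.096 (1.18) | 0.041 (0.95) |

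At a variance of 0.15 the nominal 95% interval for the rate ratio covers 1 − 0.186 = 0.81 to 1 − 0.139 = 0.86. The Monte Carlo standard error around 0.05 is √(0.05 × 0.95/700) = 0.008, so an odds-ratio error of 0.060 is not clearly above 5%.

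**Step 5: effect of a baseline covariate.** In 400 null runs of the plain negative binomial at variance 0.15, error was 21.5% unadjusted, 18% if baseline use shares half of the PCP and patient variation, and 11% if it shares all of it. At variance 0.05 with full sharing it was 8%. The degree of sharing is an assumption.

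**The case against.** The strongest reply is that this is a silence and not a decision. SAP 14.1 lists no model terms beyond treatment and nowhere says that PCP is excluded. A reader might infer that the sponsor chose to ignore clustering; the text does not show that. For the ZINB, however, the silence has a consequence, because the named procedure supplies no cluster term by default. For the SPMZINB it does not: Proc NLMIXED can carry a random intercept, so one can say only that the handling is unstated.

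A reader might also infer that every interval in the addendum is too narrow. That goes too far for the odds ratio. Its error stays near 4% if PCPs do not differ in abstinence, and the documents give no figure for that variation.

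Nor should the 18–19% of the plain negative binomial be quoted as the ZINB's error. It belongs to another model, at a variance that the SAP regards as an upper limit and without baseline adjustment. Lower variance and baseline adjustment both shrink the problem, but in the cases tried neither removes it. None of the runs includes between-imputation variance, so the size in the real pooled analysis is approximate.

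Finally, the analysis is labelled post hoc, SAP 14.1 promises intervals but no test, and no stated decision depends on it. That is correct and limits the seriousness. It does not make an interval with about 81–86% coverage acceptable under a 95% label. A reader might suspect that the addendum was written to explain or rescue the primary result; the SAP gives only the exploratory purpose, and the documents do not support more.

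**Conclusion.** The point holds for the ZINB rate ratio. Fitted as SAP 14.1 describes, its interval leaves out the cluster randomisation and is too narrow. With 60 PCPs of 5 patients and 20–40% structural zeros (assumed), type I error is about 0.14–0.19 at the SAP's upper-limit PCP variance of 0.15, and about 0.10–0.13 at an assumed 0.05. For an assumed 0.02 only the plain negative binomial was run, and it gives about 0.07–0.08. Baseline adjustment would reduce all of these.

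For the odds ratio the shortfall is conditional: about 0.06–0.09 if the logit of abstinence varies between PCPs with an assumed variance of 0.15–0.5, and none otherwise. For the SPMZINB the finding is only that the cluster handling is not stated.

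The primary analysis keeps its PCP intercept and is untouched. What suffers is the comparison between the addendum and the primary result.

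**What to change.** Amend SAP 14.1 as follows.
- Fit the ZINB in Proc NLMIXED, which the addendum already uses, with a random intercept for the PCP cluster (the PCP or team, as in SAP 7.2.2) in the count part and, if estimable, in the logit part.
- State the same cluster term for the SPMZINB.
- Carry over the site and baseline terms of SAP 7.2.2 to both models, so that they differ from the primary model only in how zeros are treated.
- If a model does not converge, use a PCP-level cluster-robust (sandwich) variance within each of the 30 imputed datasets and pool with the combination rules already in SAP 7.2.3.

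If the addendum has already been run without a cluster term, rerun it and report the clustered intervals. The cost is revised wording, a little more programming and somewhat wider intervals. No new data are needed, because the PCP cluster identifier is already in the primary analysis dataset.
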